5.4 Interim analyses

The interim analyses will be performed on all patients having completed the study before the date of the interim database extract.

5.4.1 I1: Sample size computation for the prediction of treatment efficacy

For computing the necessary sample size, a *learning curve* will be evaluated for the analysis in A3. This analysis will first be run on all patients available in the interim database extract, and the average per-treatment performance will be computed. Then a random sample of 90% of the patients will be drawn and the same analysis will be repeated. And similarly with decreasing sample size.

This will lead to a "learning curve" showing the variation of predictive performance wrt to sample size and shown in Figure (7). An extrapolation of the curve will be performed in order to estimate the expected performance obtained in the final analysis using all 140 samples. A confirmation of infirmation of the number of patients to be included in the study will be made based on this estimation

5.4.2 I2: Relation between psychological traits and pain evolution

For each feature from the patient characteristics at V1, the correlation will be computed with the linear trend of pain evolution defined in A2.1. A p-value for non-zero correlation will be reported too, with BH correction for multiple testing. Results will be presented in Table (tab-cor-baseline-pain-evol).

6 Tables, Figures and Listings requirements

6.1 Tables

All tables resulting from the analyses will be grouped in an Excel file with one worksheet per table. The worksheet names correspond to the table name mentioned in the text above. Legends for all tables will be included on top of the corresponding worksheet. The table templates used for the final results will match attached file T2001-01-SAP-table-templates-V1.xlsx

6.2 Figures

Figure 1: Outlier detection by Principal Component Analysis based on data at baseline. The two first components are represented (Variance captured: %). Colors indicate the grouping of points into clusters.

Figure 2: Matrix of correlations between all pairs of variables at baseline (personality traits and sociodemographic variables)

Figure 3: Scatterplots of the significant correlations between the different pain measures at baseline

Figure 4: Scatterplots of the significant correlations between a personality trait and a pain measure at baseline

Figure 5: Summary visualization of the evolution of pain during follow-up period. Each point represents a patient, with average APS as abscissa and linear trend as ordinate

Figure 6: Summary visualization of the evolution of analgesic treatments during follow-up period. Each point represents a patient, with the number of different analgesic drugs (for the graph on the left) or the number of different analgesic drug classes (on the right) as abscissa, and their linear trend as ordinate

Figure 7: Learning curve for the prediction of analgesic treatment efficacy. The average performance evaluated by cross-validation on random subsets of the data is shown in ordinate, with the size of the training set as abscissa. An extrapolation curve (LOWESS) is also shown for sample sizes up to N=200.

7 Data Transfer and Unblinding Plan

The study data is collected and managed by Aepodia SA. Several information transfers will occur between Aepodia and DNAlytics, under the supervision of Tools4Patient:

Jun. 2015 **Database table structure transfer** – The objective of this transfer is to allow DNAlytics to prepare the analysis scripts and finalize the SAP. The data concerning a few included patients will be transfered in order to make the scripts creation possible. Those patients data are anonymized by Aepodia prior to the transfer to DNAlytics. Those patients will however be identified by their inclusion number.

	T2001-01 – Statistical Analysis Plan	
DNAIUtics Deterdriven personalized medicine from R&D to market access		To : T4P Auth. : [name] V1.3 - 2017-04-10

May 2017 (Est.) Interim database transfer – The objective of this transfer from Aepodia to DNAlytics is to apply the interim analysis plan described in this document. Those patients data are anonymized by Aepodia prior to the transfer to DNAlytics. Those patients will however be identified by their inclusion number.

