5.3 A3: Prediction of treatment efficacy

A predictive model will be tuned based on the characteristics at V1 in order to predict the efficacy of each treatment on the patient. One model will be built for each treatment t, with the following design:

- Scope: patients having received treatment t on some but not all days
- Response (target): Per-patient treatment effect, as measured by the average difference of daily APS between the days with and without treatment t
- Predictors: patient characteristics at baseline

The performances of these pre-treatment models will be evaluated inside a resampling procedure. This procedure repeatedly samples 80% data to learn a predictive model whose predictive performances are assessed on the 20% remaining unseen data. In total, 200 train-test splits are performed for each treatment. The predictive model in use will be a ridge regression, as implemented by glmnet::cv.glmnet in R, with parameter alpha=0.

Table (tab-pred-perf) will report the average predictive performance on the test sets for each treatment, in terms of relevant statistics.

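### The interim check of the 140 completers rests on extrapolating a LOWESS curve from training sizes of at most about 48 to about 112, where LOWESS has no basis

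*SAP*

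**What the plan says.** Under SAP 5.4.1, the prediction analysis A3 is run on all interim completers and "the average per-treatment performance will be computed". The sample is then reduced: "Then a random sample of 90% of the patients will be drawn and the same analysis will be repeated", and so on downwards. The resulting curve is projected: "An extrapolation of the curve will be performed in order to estimate the expected performance obtained in the final analysis using all 140 samples". The decision follows from that projection: "A confirmation of infirmation of the number of patients to be included in the study will be made based on this estimation".

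Section 5.4.1 does not say how to extrapolate. The Figure 7 legend in SAP 6.2 does: "An extrapolation curve (LOWESS) is also shown for sample sizes up to N=200". The legend describes the vertical axis as "The average performance evaluated by cross-validation on random subsets of the data is shown in ordinate" and the horizontal axis "with the size of the training set as abscissa".

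SAP 5.3 sets the training share: "This procedure repeatedly samples 80% data to learn a predictive model". It fits one model per treatment, using only patients who were on that treatment for part of their days. It leaves the performance statistic unnamed.

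The SAP introduction places the interim at 60 completers, and protocol 4.2.3 at approximately 60. Protocol 4.2.3 allows two outcomes: the planned size is confirmed, or it is lowered if strong relations with pain outcomes appear for enough patient features. Protocol 4.2.1 states that 140 was not derived from a hypothesis test or a precision target.

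**The concern.** The decision needs a predicted performance well beyond any training size that the interim can observe. LOWESS fits a weighted line or parabola to neighbouring points. Beyond the last point there are no neighbours on one side, and nothing in the method encodes the flattening expected of a learning curve. The predicted value is then whatever the last few points imply, under a span and local degree that the SAP does not state.

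Other gaps leave the estimate open to choices made after the data are seen:

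- The legend uses training-set size, but 5.4.1 speaks of all 140 samples.
- Section 5.4.1 reads as one random draw per size, the legend as several.
- No performance measure, interval or decision threshold is given.

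At stake is a decision on the number of patients in a study whose sample size has no formal calculation behind it.

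**Working it through.** **The planned figure.** The 140 has no formula or power inputs, so it cannot be reproduced. What can be checked is whether the stated method can inform it.

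**Inputs from the documents.** 60 interim completers; 140 final completers; 80% training share; figure drawn to N = 200.

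**Extrapolation distance.**

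- Largest observed training size: 0.8 × 60 = 48.
- Target training size: 0.8 × 140 = 112.
- Ratio: 112 / 48 = 2.33.
- With subsamples from 30% to 100% (assumed), the observed range is 14.4 to 48, a width of 33.6. The target lies 112 − 48 = 64 beyond it, or 64 / 33.6 = 1.9 widths.
- N = 200 is a training size of 0.8 × 200 = 160, or 200 if read directly off the axis.
- If half the patients qualify for a treatment's model (assumed), the sizes are 24 and 56, with the same ratio.

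The 48 is approximate: the extract may hold slightly more than 60 completers, while the per-treatment scope makes actual sizes smaller.

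**Software behaviour.** In R 4.3.3, lowess() has no argument for new sizes and returned only the observed range. Default prediction from loess() gave NA at 60, 112 and 160. The lowess function in Python's statsmodels does return values outside the range, by extending a local line.

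**Noise-free curves (assumed).** Power law P(n) = 0.30 − 1.6·n^(−0.75); exponential P(n) = 0.255 − 0.45·exp(−n/25). Both give 0.25 at n = 112. The loss from 140 to 100 completers is P(112) − P(80), with 0.8 × 100 = 80.

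| Quantity | Truth | Local-linear, power law (span 2/3; 1) | Local-linear, exponential (span 2/3; 1) |
|---|---|---|---|
| Performance at 112 | 0.25 | 0.32; 0.35 | 0.40; 0.44 |
| Loss from 112 to 80 | 0.013 | 0.053; 0.065 | 0.10; 0.12 |

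A forced local-quadratic fit to the power law gives 0.14 (span 2/3) or 0.05 (span 1) at 112, below the truth. The sign of the error therefore depends on a setting that the SAP leaves open.

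**Adding noise to each point (power law, local-linear, 3,000 runs per cell).** The truth is 0.25.

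| Noise SD | 95% range at 112, span 2/3 | 95% range at 112, span 1 | Runs where fewer patients look as good or better (span 2/3; 1) |
|---|---|---|---|
| 0.005 | 0.23 to 0.41 | 0.30 to 0.40 | 1%; 0% |
| 0.01 | 0.14 to 0.50 | 0.26 to 0.45 | 11%; 0% |
| 0.02 | −0.04 to 0.69 | 0.17 to 0.54 | 27%; 6% |

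A fresh run reproduced the noise-free values, and the noise ranges and percentages closely.

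**Patient-level simulation (assumed).** 60 patients, 20 predictors, true R² 0.30, ridge regression, 8 subsamples per size. Performance is 1 minus squared error relative to predicting the training mean. The closer analogue of the SAP averages four treatment models, each on half the patients. True performance at 140 is 0.12.

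- LOWESS ranged from −0.62 to 0.93 (span 2/3, RMSE 0.39) or −0.47 to 0.53 (span 1, RMSE 0.26).
- A bounded power law ranged from −0.16 to 0.18 (RMSE 0.18). It is tighter but centred near 0.01, so biased low.
- The true loss from 140 to 100 is 0.059. At a margin of 0.02, a reduction was wrongly supported in 25% or 27% of interims by LOWESS (spans 2/3 and 1) and in 27% by the upper limit of the parametric loss. At a margin of 0.05 the rates were 33% or 37%, against 52%.
- Adding the requirement that the lower limit of interim performance beat a model without predictors brought the parametric rule to 0% at both margins.

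**The case against.** The strongest reply is that the systematic error does not lead to the harm. Without noise, local-linear LOWESS shows a loss from stopping early of 0.053 to 0.12 against a true 0.013, which argues for keeping 140. That stands. A wrong reduction arises through noise, and how often depends on assumed noise, span and margin; at span 1 and noise SD 0.01 it was 0%.

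Second, the protocol already limits the harm. A decrease requires strong relations for enough features, SAP I2 supplies feature correlations corrected for multiplicity, and protocol 4.2.3 requires an approved amendment for substantial changes. This stands in part: SAP 5.4.1 nevertheless bases its decision on the extrapolated value.

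Third, a parametric curve is not shown to make better decisions in the per-treatment design. That stands too. Its upper limit did no better at margin 0.02, did worse at 0.05, and missed the true loss in 60% of runs.

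Fourth, LOWESS appears only in a legend, and R is named only for the ridge model. But Figure 7 is the figure that 5.4.1 cites for this curve, and neither document names another extrapolation method. Missing values in R are an implementation matter; the lack of any basis beyond the data is not.

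**Conclusion.** The stated method cannot deliver the estimate on which SAP 5.4.1 bases its decision. The gap from about 48 to about 112 follows from the documents, and the R behaviour was observed directly. The sizes of bias and instability rest on assumed curves, noise and simulation settings: 0.32 to 0.44 against 0.25 for local-linear fits, an error in the other direction for local-quadratic fits, and 95% ranges up to −0.04 to 0.69 at noise SD 0.02.

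Three stronger readings are not supported. A reader might infer that LOWESS always overstates performance at 140; the direction changes with local degree, and in the per-treatment simulation at span 1 the range was centred near 0.03, below the true 0.12. A reader might infer that the plan is tilted towards stopping early; the noise-free local-linear error points the other way. A reader might infer that 140 is too few; nothing here shows that.

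This should be corrected before the interim transfer. It does not invalidate the study, which is observational, and whose interim can only confirm or lower the number.

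**What to change.** **Figure 7 legend.** Replace the last sentence with: *LOWESS is drawn only within the observed training-set sizes. Beyond them a parametric learning curve a − b·n^(−c), with bounds for a, b and c fixed before the interim transfer, is shown with a patient-level resampling interval. The interval is approximate; its coverage may be poor where per-treatment samples are small.* A delete-group jackknife over patients would serve. An ordinary bootstrap could put copies of one patient in both training and test sets.

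**SAP 5.4.1.**

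- Use training-set size throughout. The target is 80% of the final number in each treatment's model (112 if all 140 contribute).
- Name one performance measure, for example squared error relative to predicting the training mean.
- Average repeated random subsamples at each size, for example 8 or more.
- Add: *140 is kept unless (1) the upper limit of the loss in performance at the reduced number is below a margin fixed before the interim, and (2) the lower limit of performance at the interim size is better than a model without predictors.*

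The protection comes mainly from condition (2), which is in the spirit of the protocol's own condition for a reduction, and not from the parametric curve.

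**Cost.** A few lines of SAP text and code, and no new data. The sponsor must choose a margin in advance. The real price is that the interim will usually only confirm 140: at true R² 0.30, condition (2) was met in 3% of simulated interims with one model on all patients and in 0% with four treatment models.
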